8.2.2 Placebo - Comparator

Substance (INN):	Not applicable
Pharmaceutical Form:	Soft gelatine capsule
Source:	Boehringer Ingelheim Pharma GmbH & Co. KG
Unit Strength:	Placebo contains 0 mg of nintedanib in capsules matching 100 mg and 150 mg of nintedanib
Daily Dose:	Matching capsules orally twice daily, dose reduction according to Section Error! Reference source not found.
Duration of Use:	Continuous daily dosing until progression of disease (see exception regarding brain metastases in Section 7.3.5) or until criteria for interruption of treatment is met. The maximum time on treatment will be 6 months.
Route of Administration:	Oral
Posology:	Twice daily (to be swallowed whole, with a glass of liquid of about 250 mL with a dose interval of 12 hours at the same times every day, usually in the morning and the evening after food intake)

8.3 Storage and Stability

The Investigator or designate will be responsible for ensuring that the investigational product is securely maintained in a locked, limited-access facility, as specified by Boehringer Ingelheim and in accordance with the applicable regulatory requirements.

The current shelf life for all dosage strengths and formulations is 60 months. The capsules are packaged in child resistant high density polyethylene (HDPE) bottles, and have to be stored below 30°C.

Refer to the Investigator's brochure for full details on storage requirements and stability.

Drug storage temperature will be maintained and recorded, as applicable.

8.4 Handling and Disposal

The Investigator or designee will be responsible for dispensing and accounting for all investigational drug provided by Boehringer Ingelheim exercising accepted medical and pharmaceutical practices. Study drugs must be handled as cytotoxic agents and appropriate precautions taken per the institution's environmentally safe handling procedures. All investigational drugs will be dispensed in accordance with the Investigator's prescription or written order.

All products dispensed will be recorded on a product accountability record. Records of product lot numbers and dates received will be entered on a product accountability form. This record will be reviewed by the Sponsor's staff or representative during periodic monitoring visits. It is the Investigator's responsibility to ensure that an accurate record of investigational drug issued and returned is maintained.

Unused/expired capsules will be destroyed according to standard practices after properly accounting for the dispensing. Partially used vials of study drug will not be re-used for other participants.

Under no circumstances will the Investigator supply investigational drug to a third party or allow the investigational drug to be used in a manner other than as directed by this protocol.

8.5 Treatment Unblinding

Treatment unblinding may occur only if the knowledge of treatment assignment will materially change the planned management of a medical emergency. Envelopes containing treatment arm information (drug versus placebo) will be stored at the site pharmacy. Given the constitution of the drug, unblinding is not anticipated for any circumstance. Any request for unblinding should be discussed with the sponsor's medical monitor, [name].

8.6 Durvalumab

Durvalumab is commercially available and will be dispensed per standard of care. Durvalumab will not be provided by this study and will be paid for by the patient's insurance carrier as part of standard of care treatment post chemo-radiation.

9 STUDY PROCEDURES

Unless otherwise defined in the written protocol text, all procedures/assessments will be conducted in accordance with RPCI Clinical Research Services Standard Operating Procedures.

9.1 Participant Randomization and Registration

Phase I:

Subjects enrolled to the dose escalation portion of the study will NOT undergo randomization (i.e. not blinded to treatment) and will receive the active drug nintedanib according to the dose level assigned.

Phase II:

Patients will be randomized, by site, at the baseline visit into one of 2 arms, placebo or nintedanib, in a 1:2 fashion using a block-permutation design, but this will be masked to the investigator and patient. The randomization list will be generated by the study biostatistician.

Patients will be included in data analyses according to their randomized treatment assignment irrespective of the treatment actually received (intent-to-treat).

Patients will be assigned a study number in the order of randomization.

No study-specific procedures are to be performed until informed consent is obtained. Eligibility of each patient will be established prior to study enrollment.

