6 PARTICIPANT SELECTION

6.1 Inclusion Criteria

- 1 Age 18 years or greater.
- 2 Histologically or cytologically-proven non squamous cell NSCLC. Mixed histology with SCLC component not allowed.
- 3 Patients with Stage II - IV non squamous cell NSCLC who received at least 54 Gy of total planned thoracic radiation dose will be eligible. Patients must have received at least one cycle of chemotherapy concurrently during the course of thoracic radiation. Regimens allowed are platinum combinations with either etoposide or a taxane regardless of histology subtype; platinum with pemetrexed for patients with nonsquamous NSCLC only. Patients with oligometastatic Stage IV cancer are eligible if they have received only one line of systemic therapy for their Stage IV cancer prior to the concurrent chemoradiation phase.
- 4 Patient must have had a CR/PR/SD, 4-6 weeks after completing last fraction of radiation therapy.
- 5 ECOG Performance Score 0 - 2 (**Appendix C**).
- 6 ANC $\geq 1,500/\mu\text{L}$.
- 7 Platelet count $\geq 100,000/\mu\text{L}$.
- 8 Hemoglobin ≥ 9 g/dL.
- 9 Total bilirubin \leq normal or for those with Gilbert's syndrome ≤ 1.5 times upper limit of normal (ULN) OR direct bilirubin normal (per institute standards).
- 10 AST $\leq 1.5 \times$ ULN. ALT and AST $\leq 2.5 \times$ ULN is acceptable if there is liver metastasis.
- 11 Fertile patients must use adequate contraception.

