6.2 Exclusion Criteria

- 1 WBRT < 14 days from the anticipated start of nintedanib/placebo administration.
- 2 Squamous cell NSCLC

- 3 Unable to start nintedanib/placebo treatment between 4 – 8 weeks after completing the last dose of thoracic radiation.
- 4 Active untreated brain or leptomeningeal metastases. In patients with treated CNS metastases, eligible if symptoms controlled for at least 4 weeks. Dexamethasone allowed if total daily dose does not exceed 2 mg.
- 5 Major injuries or surgery (e.g., craniotomy) <28 days from the start of nintedanib/placebo administration. Wound should be healed prior to starting therapy.
- 6 Second malignancies are allowed as long as the disease does not require active treatment with concomitant systemic cytotoxic chemotherapy, investigational or biologic therapy (e.g., anti-CTLA4 or HER2 monoclonal antibodies). Hormone-related therapies (e.g., LHRH agonists, tamoxifen, etc.) are allowed.
- 7 Concurrent uncontrolled illness including, but not limited to, ongoing or active infection, symptomatic congestive heart failure, unstable angina pectoris, cardiac arrhythmia, or psychiatric illness/social situation that would increase the risk associated with study participation and/or limit compliance with study requirements.
- 8 Inability to swallow study medication.
- 9 Presence of active malabsorption disorder (e.g., flare episodes documented within the preceding 3 months, presence of symptoms requiring daily medications for control) or history of extensive small bowel resection.
- 10 Known bleeding or thrombotic diathesis.
- 11 History of arterial or venous thromboembolic event within 12 months prior to study participation.
- 12 Active hemoptysis or history of clinically relevant hemoptysis as determined by the treating physician. Patients who had history of transient minor hemoptysis after bronchoscopic biopsy are eligible unless deemed otherwise by the treating physician.
- 13 CTCAE Grade 2 or higher proteinuria.
- 14 Investigational agent administered < 28 days prior to treatment with nintedanib. Last dose of systemic chemotherapy administered < 14 days prior to treatment with nintedanib.
- 15 Known chronic active hepatitis B or hepatitis C. HIV-positive patients receiving or are candidates for antiretroviral therapy are also excluded.
- 16 Pregnancy or breast feeding. Female patients with child-bearing potential must have a negative pregnancy test (β -HCG test in urine or serum) prior to commencing study treatment.

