9.2 Baseline Evaluations

The following will be performed within 4 weeks prior to first dose of study drug:

- Medical history
- Smoking History (Type of Tobacco/Nicotine Product [cigarettes, cigars, pipes, chew tobacco, nicotine gum, nicotine patch, other], current use, how long ago product use stopped.)
- Physical examination, including vital signs (i.e., temperature, heart rate, respiratory rate, blood pressure, body weight, and height)
- Hematology [(i.e., complete blood count (CBC) with automated differentials)](or, the physicians' discretion): WBC, RBC, HGB, HCT, platelet, MCV, MCH, MCHC, % neutrophils, absolute neutrophils, % monocytes, absolute monocytes, % eosinophils, absolute eosinophils, % basophils, absolute basophils, % lymphocyte total, absolute lymphocyte total, platelet confirmation (as clinically indicated), and differential confirmation (as clinically indicated). Note: Participants experiencing Grade 4 neutropenia should be monitored according to institutional guidelines. As needed at each study visit as determined by the Investigator or study physician.
- Chemistry (i.e., complete metabolic panel (CMP): chloride, CO₂, potassium, sodium, BUN, glucose, calcium, creatinine, total protein, albumin, total bilirubin, alkaline phosphatase, AST, ALT, A/G ratio, BUN/creatinine ratio, osmol (Calc), anion gap).
- Pulmonary Function Test
- ECOG Performance Status (Appendix C)
- Urinalysis to assess proteinuria
- Tumor/Disease Assessment

- Concomitant Medications: List any ongoing medications with an onset within 1 week of first dose of study drug.
- Adverse Events

9.3 Evaluations Performed at Cycle 1 Day 1

The following will be performed on Cycle 1 Day 1 or within 7 days prior to drug administration:

- Medical history
- Physical examination, including vital signs (i.e., temperature, heart rate, respiratory rate, blood pressure, and body weight)

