- Hematology [(i.e., complete blood count (CBC) with automated differentials)](or, the physicians' discretion): WBC, RBC, HGB, HCT, platelet, MCV, MCH, MCHC, % neutrophils, absolute neutrophils, % monocytes, absolute monocytes, % eosinophils, absolute eosinophils, % basophils, absolute basophils, % lymphocyte total, absolute lymphocyte total, platelet confirmation (as clinically indicated), and differential confirmation (as clinically indicated). Note: Participants experiencing Grade 4 neutropenia should be monitored according to institutional guidelines. As needed at each study visit as determined by the Investigator or study physician.
- Chemistry (i.e., complete metabolic panel (CMP): chloride, CO₂, potassium, sodium, BUN, glucose, calcium, creatinine, total protein, albumin, total bilirubin, alkaline phosphatase, AST, ALT, A/G ratio, BUN/creatinine ratio, osmol (Calc), anion gap).
- 25-OH Vitamin D level (one 3 mL gold-top tube)
- Mitochondrial DNA Assay (one 10 mL heparinized green-top tube)
- miRNA Biochip Assay (one 10 mL red-top tube)
- QOL Questionnaire (Appendix F)
- Pregnancy Test (Urine or Serum) for females of child-bearing potential
- ECOG Performance Status (Appendix C)
- Dispense nintedanib/Placebo
- Concomitant Medications
- Adverse Events

9.4 Evaluations Performed on Day 1 of Cycle 2 through Cycle 6

- Medical history
- Physical examination, including vital signs (i.e., temperature, heart rate, respiratory rate, blood pressure, and body weight)
- Hematology [(i.e., complete blood count (CBC) with automated differentials)](or, the physicians' discretion): WBC, RBC, HGB, HCT, platelet, MCV, MCH, MCHC, % neutrophils, absolute neutrophils, % monocytes, absolute monocytes, % eosinophils, absolute eosinophils, % basophils, absolute basophils, % lymphocyte total, absolute

lymphocyte total, platelet confirmation (as clinically indicated), and differential confirmation (as clinically indicated). Note: Participants experiencing Grade 4 neutropenia should be monitored according to institutional guidelines. As needed at each study visit as determined by the Investigator or study physician.

- Chemistry (i.e., complete metabolic panel (CMP): chloride, CO₂, potassium, sodium, BUN, glucose, calcium, creatinine, total protein, albumin, total bilirubin, alkaline phosphatase, AST, ALT, A/G ratio, BUN/creatinine ratio, osmol (Calc), anion gap).
- Mitochondrial DNA Assay (Cycle 3 and Cycle 6 only) (one 10 mL heparinized green-top tube)

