13.1 Sample Size Determination

A maximum of 18 participants will be enrolled to the non-randomized dose escalation portion of this study. The number of participants required is a function of the unknown dose-toxicity relationship.

A maximum of 99 participants will be enrolled to the randomized Phase 2 portion of this study (excluding patients replaced due to ineligibility or inability to start therapy). Participants will be randomized in a 1:2 fashion, stratified by chemotherapy regimen (i.e., platinum with etoposide, platinum with taxane, platinum with pemetrexed) and immune therapy (i.e. durvalumab), into the placebo and nintedanib arms. Accrual is expected to take 4 years.

Evaluable patients will be any patient who receives at least one dose of study drug.

The sample size justification is based on the primary analysis: a comparison of the rate of radiation pneumonitis at 6 months after completion of chemoradiation between the placebo and nintedanib arms, stratified by chemotherapy regimen (i.e., platinum with etoposide, platinum with taxane, platinum with pemetrexed) and immune therapy exposure (i.e. durvalumab), using the one-sided Cochran-Mantel-Haenszel (CMH) exact test at a significance level of 0.05. The expected rate of Grade 2 or higher radiation pneumonitis is 30% in the placebo arm, and a decrease in this rate to 10% in the nintedanib arm would be considered clinically significant; which is equivalent to a common odds ratio (COR) of approximately 0.26.

Using a simulation based on the proposed study design; if there is no improvement in the rate of radiation pneumonitis (COR = 1.0), then there is a 59.0% chance of stopping early for futility. If the true COR is 0.26, then there is only a 10.6% chance of stopping early for futility. If the true common odds ratio is 0.26, then there is an 80.1% chance of detecting a significant reduction in the rate of Grade 2 or higher radiation pneumonitis in the nintedanib arm. If the COR is 1.0, then the chance of detecting a significant reduction is 4.2%; which can be considered the effective type-I error rate.

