3. PARTICIPANT REGISTRATION

The participant completes the Gender, Race, and Ethnicity Form and this is placed in the study binder.

RPCI does not grant exceptions to eligibility criteria.

Phase 1 Protocol Registration Instructions

Contact the RPCI Network Monitor to verify that a slot is available in the open cohort when a participant has been identified. **Do not have the participant sign consent prior to verifying an open slot.**

- After the participant signs consent, the Subject Screening and Enrollment Log must be faxed or emailed to the RPCI Network Monitor within 1 business day. The RPCI Network Monitor

will confirm receipt of the Subject Screening and Enrollment Log and email the participant ID number.

- When the participant has met eligibility, a signed eligibility checklist and other requested documentation will be faxed or emailed to the RPCI Network Monitor.
- Within 1 business day of receipt of the eligibility check list, the RPCI Network Monitor will fax or email the cohort assignment and dose level.
- An email must be sent by the site to confirm receipt of the cohort assignment and to provide the planned treatment start date.

Phase 2 Protocol Registration Instructions

The Subject Screening and Enrollment Log must be faxed or emailed to the RPCI Network Office within 1 business day of the date the participant is consented. Once the Investigator has determined that eligibility has been met, complete the eligibility check list and fax or email it to the RPCI Network Monitor at [contact].

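### Randomisation at the baseline visit can precede first dose by up to about 4 weeks and precede the pregnancy test, which can add post-randomisation exclusions and non-starters whose place in the intent-to-treat analysis is not settled

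*Combined protocol and SAP*

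**What the plan says.** **Time of randomisation.** Section 9.1 (Phase II): "Patients will be randomized, by site, at the baseline visit into one of 2 arms".

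**Baseline window.** Section 9.2 heads its list with "The following will be performed within 4 weeks prior to first dose of study drug". Table 5, footnote 1, gives the same window.

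**Eligibility first.** Section 9.1 also says "Eligibility of each patient will be established prior to study enrollment". Appendix A, Participant Registration (Phase 2), has the same order: "Once the Investigator has determined that eligibility has been met, complete the eligibility check list".

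**Pregnancy test.** Exclusion 16 (section 6.2) requires a negative result "in urine or serum) prior to commencing study treatment". Section 9.3 and Table 5 list the test only at Cycle 1 Day 1, which may be up to 7 days before dosing: "Pregnancy Test (Urine or Serum) for females of child-bearing potential". It is not among the baseline evaluations in 9.2.

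**Time from radiation.** Inclusion 4 reads "Patient must have had a CR/PR/SD, 4-6 weeks after completing last fraction of radiation therapy". Exclusion 3 rules out patients who cannot start study drug between 4 and 8 weeks after radiation.

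**Who is counted.** Sections 9.1, 13.3 and 13.5 specify intent-to-treat. Section 13.1 sets the maximum of 99 "excluding patients replaced due to ineligibility or inability to start therapy", and defines evaluable patients as those with at least one dose.

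**The concern.** In a double-blind prevention trial, randomisation normally comes after the last entry result and as near to first dose as is practical. Anything that happens in between belongs to a randomised patient and, under intent-to-treat, stays in the comparison. Here the two steps are separated, no maximum gap is stated, and one entry test is scheduled at the later step.

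Two things are at stake. First, some patients may be found ineligible, or become unable to start, after they have been allocated. The plan both replaces them and promises intent-to-treat, without saying whether a replaced patient remains in the primary analysis. Second, pneumonitis that is already present or developing may not be recorded before allocation. The plan does not say how a Grade 2 or higher event before first dose is treated, and no eligibility criterion names existing pneumonitis.

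**Working it through.** **1. Largest gap the windows allow.** Inputs: earliest response assessment at week 4 (inclusion 4), latest start at week 8 (exclusion 3), baseline at most 4 weeks before dosing (9.2).

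- Response assessed at week 4, first dose at week 8: 8 − 4 = 4 weeks, which is also the 9.2 limit.
- Response assessed at week 6, first dose at week 8: 8 − 6 = 2 weeks.
- Baseline and Cycle 1 Day 1 assessments done together: 0 weeks.

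So the range is 0 to about 4 weeks. The upper end needs the earliest response assessment and the latest start in the same patient. Section 13.3 says only that treatment starts within the eligibility timeframe. The synopsis instead ties the start to the onset of symptoms, at the patient's discretion. Those two statements contradict each other and must be reconciled.

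**2. How long the pregnancy result can be outstanding.** Section 9.3 allows the test from 7 days before dosing. If randomisation is 28 days before dosing, the earliest scheduled test comes 28 − 7 = 21 days after randomisation, and the latest comes 28 days after it. If the baseline visit falls within 7 days of dosing, both can be done together and the problem disappears.

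**3. Which entry tests are affected.** Haematology, chemistry, urinalysis, performance status and tumour assessment are all in the 9.2 baseline list. The Cycle 1 Day 1 blood counts, chemistry and performance status are repeats. Only the pregnancy test is listed solely after baseline.

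**4. What the unsettled analysis set amounts to.** The plan gives no non-start rate. Assume a share r of randomised patients is replaced and 99 others are counted. The number replaced is 99 × r/(1 − r):

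| r (assumed) | Replaced patients |
|---|---|
| 3% | 99 × 0.03/0.97 = 3.1 |
| 5% | 99 × 0.05/0.95 = 5.2 |
| 10% | 99 × 0.10/0.90 = 11.0 |

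The plan's odds ratio for 30% against 10% reproduces: (0.10/0.90)/(0.30/0.70) = 0.259, stated as approximately 0.26. If a share r of the nintedanib arm never starts, is kept in the analysis and has the placebo rate (an assumption), the arm's rate is 0.30r + 0.10(1 − r):

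- r = 5%: 0.015 + 0.095 = 11%, odds ratio (0.11/0.89)/(0.30/0.70) = 0.29.
- r = 10%: 0.030 + 0.090 = 12%, odds ratio (0.12/0.88)/(0.30/0.70) = 0.32.

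The two readings of the analysis set therefore estimate different quantities. How much of r is due to early randomisation cannot be derived from the documents.

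**The case against.** **Eligibility is meant to come first.** Section 9.1 and Appendix A both put eligibility ahead of enrolment, and the eligibility form forbids enrolling a patient who fails any criterion. On that reading, randomisation waits for the baseline results. This stands for every test in 9.2. A reader might infer that patients are randomised before the entry tests in general are done, but the documents support this for the pregnancy test alone. Even there, exclusion 16 asks only for a result before treatment, and only in women of child-bearing potential. What remains is a narrow scheduling conflict.

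**Replacement protects the number treated, and masking limits bias.** Both are true. Because allocation is masked, failure to start should not depend on arm. The issue is mainly an undefined analysis set and lost information; the documents give no reason to expect bias towards one arm.

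**Dilution of the treatment effect.** A reader might infer a definite loss of power from pneumonitis between randomisation and first dose. For example, spreading a 30% placebo rate evenly over 26 weeks, with a 4-week gap and a two-thirds reduction only after dosing, gives 0.30 × 4/26 + 0.30 × (22/26)/3 = 13.1% on nintedanib instead of 10%. The documents do not support this inference:

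- They say nothing about when events occur; the even spread is assumed.
- The endpoint clock starts at completion of chemoradiation (13.5) and drug starts 4-8 weeks later. Under the same even spread, 4/26 = 15% to 8/26 = 31% of placebo events precede first dose whenever randomisation takes place. Moving randomisation changes neither date, and no criterion naming pneumonitis would exclude those patients.
- The 10% target in 13.1 is a rate at 6 months after chemoradiation, so it may already include pre-dose events.

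The objection therefore defeats any power or futility figure attached to randomisation timing. It does not answer the missing cap on the gap, the pregnancy-test conflict or the unsettled status of replaced patients.

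**Conclusion.** The point holds in limited form. As written, 9.1 permits randomisation up to about 4 weeks before first dose. In that extreme case, it comes 3 to 4 weeks before the scheduled pregnancy test, contrary to the plan's own rule that eligibility comes first. Early randomisation leaves room for post-randomisation ineligibility and failure to start, and 13.1 handles these by replacement in a way that does not fit the intent-to-treat statements.

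The 4-week figure is a maximum. The typical gap, the number of women affected and the non-start rate are not given. The counts of 3 to 11 replaced patients rest on assumed rates of 3% to 10%, only some unknown part of which would be due to timing. No change in the stated power or futility probabilities follows. This is a worthwhile and inexpensive improvement, and it does not invalidate the design.

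**What to change.** - **Section 9.1:** instead of the baseline visit, randomise once the signed eligibility checklist and all entry results, including the pregnancy test, are available, on Cycle 1 Day 1 or within a few days before.
- **Section 9.3 and Table 5:** schedule the pregnancy test before randomisation.
- **Sections 9.2 and 13.5:** record pneumonitis status and grade before allocation, and state how pneumonitis arising before first dose is counted in the primary analysis. Moving randomisation makes these events visible before allocation but does not by itself settle how they count.
- **Sections 13.1 and 13.5:** keep all randomised patients in the intent-to-treat set, including any who are replaced, and say what the at-least-one-dose definition is used for.
- **Synopsis and section 13.3:** reconcile the two statements on when study treatment starts after randomisation.

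**Cost.** A few sentences, and a shorter turnaround for randomisation and pharmacy. Randomisation is already electronic and done by one department (13.3), and adverse events are already recorded at baseline (9.2). Network sites send checklists by fax or email, so each would need to confirm that the shorter interval is workable; the documents give no pharmacy turnaround time.
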